#### Nervous system disorders

5. Grade 3 CNS disorder lasting > 7 days that is not present at baseline and is not attributable to the location of the tumor or the neurosurgery.
6. Second occurrence of a grade 3 CNS disorder that is not present at baseline and is not attributable to the location of the tumor or the neurosurgery.
7. Any grade 4 CNS disorder that is not present at baseline and is not attributable to the location of the tumor or the neurosurgery.

#### Non-hematological, non-nervous system toxicities

8. Grade 3 toxicity despite maximal medical therapy lasting > 7 days.

9. Grade 3 toxicity resulting in study agent discontinuation (permanently removed from study treatment).
10. Grade 4 toxicity, except grade 4 diarrhea that responds to maximal medical therapy within 3 days.

Please note: An allergic reaction to the NSCs is excluded from the DLT definition, because NSC dose reduction is not appropriate in this situation. The possible occurrence of allergic reactions to the NSCs is addressed by the study stopping rules (Section 5.6).

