### 5.1.2 Phase I Cohorts and Dose Escalation and De-escalation Criteria

Phase I Cohorts will be of 3 or 6 participants, as indicated by the dose-escalation criteria.

**Enrollment of the first 3 patients to a dose level will be staggered** by requiring that each of the first 3 patients be separately observed for 4 weeks (or until the DLT assessment period has ended) before the next patient can start treatment on that dose level.

Dose escalation will proceed through the identified doses without skipping any dose levels.

**To be counted for dose escalation**, a study patient must receive at least 80% of the assigned NSCs and 80% of the irinotecan for a particular dose level and be followed for 4 weeks OR have experienced a DLT as defined in Section 5.3.3.

All study patients enrolled are to be fully followed for toxicity; any study participant who is not evaluable for dose escalation will be replaced.

The NSC dose levels and irinotecan dose schedules are provided in Table 5.3.1. The first cohort will start at NSC dose level 1 and irinotecan schedule A.

The following dose escalation rules will be used, using the DLT definition as provided in Section 5.3.2:

- If 0/3 study participants experiences a DLT, the next cohort of 3 study patients will be treated at the next higher dose level.
- If 1/3 study participants experiences a DLT, the cohort will be expanded by another 3 study participants who will be treated at the same dose level for a total of 6 study participants.
- If 1/6 participants experiences a DLT, the next cohort of 3 study participants will be treated at the next higher dose level.
- If 2 or more participants of either a 3 participant or 6 participant cohort encounter a DLT, then the MTD has been exceeded. If applicable, three (more) participants will be enrolled at the next lower dose level.
- At least 6 patients will be treated at the MTD (or MFD, if the MTD is not reached).

If the 3+3 design rules indicate a need for de-escalation, the following will apply:

- If all DLTs in a dose level are attributed uniquely to irinotecan, then only the irinotecan schedule will de-escalate.
- If all DLTs in a dose level are attributed uniquely to NSCs, and are not attributed to 'NSCs with irinotecan', nor to irinotecan alone, then only the NSC dose level will de-escalate.

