#### Discontinuation toxicities

1. Receives less than 80% of study treatments due to a toxicity related to NSCs or irinotecan, except CNS toxicities that are present at baseline and attributable to the location of the tumor or the neurosurgery.

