#### 5.1.4 Definition of Maximum Tolerated Dose and Maximum Feasible Dose

---

The MTD/MFD will be based on the assessment of DLTs as defined in Section 5.3.3. The MTD is the dose level at which 0/6 or 1/6 participants experience a DLT with the next higher dose having at least 2/3 or 2/6 participants encountering a DLT. If the MTD has not been reached with NSC dose level 4 and irinotecan schedule A, then that dose level will be termed the maximum feasible dose (MFD).

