#### **Treatment Plan: Expansion Cohort**

---

After the MTD/MFD of the combination therapy is defined, an expansion cohort of 8 patients will be treated to gain more experience regarding the tolerability of study treatment at the MTD/MFD and to assess the biological activity of the hCE1m6-NSCs using intracerebral microdialysis. Since it is anticipated that the MTD/MFD will be 150 million NSCs (dose level 4), the 6 patients who will be treated on dose level 4 will undergo intracerebral microdialysis and be counted as part of the expansion cohort.

Four patients in the expansion cohort will undergo intracerebral microdialysis after receiving NSCs at the time of surgery followed 2 days later by IV irinotecan, but the other 4 patients in this cohort will not receive NSCs on the day of surgery. Instead they will be given IV irinotecan 2 days after surgery, and dialysate samples will be collected from them to determine how much SN-38 is present in the brain from treatment with IV irinotecan alone. These 4 patients will then receive their first dose of NSCs through the Rickham on day 15 of cycle 1 followed by irinotecan on day 17.

To determine who will receive their initial NSCs administration on the day of surgery, and who will receive their first NSC administration on Day 15 via the Rickham catheter, participants will be stratified according to surgery type (craniotomy or biopsy), and, as each group enrolls participants, it will alternate between enrolling the participant to the Day 1 NSC start date and the Day 15 NSC start date. For example, the first craniotomy participant will be assigned Day 1 NSC start date, the second craniotomy participant will be assigned Day 15 NSC start date, the third will be assigned Day 1 NSC start date, the fourth will be assigned Day 15 NSC start date, and so on as applicable. The same alternate enrollment scheme will apply to participants undergoing the biopsy procedure. The rationale for this plan is to ensure to the degree possible an even distribution of start dates for each surgery group which should increase the ability for direct comparison. There is no requirement for specific number of biopsy or craniotomy participants in the expansion cohort.

If the DLT rate in the expansion cohort exceeds 34%, the toxicity data will be reviewed.

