### **Study Stopping Rules**

The study will be discontinued if i) the incidence of DLT level toxicities that are probably or definitely attributable to the NSCs or NSCs and irinotecan in study patients exceeds 50% in more than 6 patients, or ii) two grade 4 allergic reactions that are probably or definitely related to NSCs. Note death from tumor progression will be scored as a grade 5 toxicity (with very low level of attribution—unlikely or not related), and only deaths occurring < 30 days from intracerebral administration of NSCs will be considered for the purposes of defining conditions for discontinuation of the study.

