### 7.1.5 General Information

---

1. The study will use the NCI Common Terminology Criteria for Adverse Events (CTCAE) version 4.0 to grade toxicities. A copy of the version 4.0 can be downloaded from:  
<http://evs.nci.nih.gov/ftp1/CTCAE/About.html>
2. Whenever treatment is held pending resolution of toxicity to grade 1 or return to baseline, this criterion may also be met if the toxicity resolves to within 1 grade of the baseline value for a pre-existing laboratory abnormality. Baseline values are from screening assessments.
3. Study agents are always held together, regardless of the attribution of the toxicity.
4. NSC or irinotecan dose re-escalation is never permitted in this study.
5. If, for the best interest of the patient, the investigator wants to hold the study agent(s) or dose reduce (including increasing the dose reduction) after an adverse event in a manner not outlined in Table 7.2.4, this is permissible following discussion with and written approval the Principal investigator.\*
6. For situations where a participant experiences a toxicity which the treating investigator feels is unlikely related to treatment with either study agent, but which requires hold or reduction of either agent according to Table 7.2.4, maintaining treatment or maintaining treatment dose is allowable per discussion with and written approval by the Principal Investigator.\*
7. For holds due to toxicities related to study agent(s), if the participant does not meet criteria to resume treatment within 28 days of their last NSC administration (or irinotecan for Dose Level 1/1 participants after they have completed cycle 1), the participant must permanently discontinue study treatment (both agents). However, if the participant is clearly benefiting from the study, the investigator may contact the Principal Investigator to determine if the participant can remain on study and at what dose level. Agreement of the Principal Investigator is to be documented in writing.\*
8. For holds for reasons other than treatment related toxicities, such as inclement weather or adverse events unrelated to study agents, if the participant does not meet criteria to resume treatment within 28 days of their last NSC administration, the study agent(s) may be restarted with written approval from the Principal Investigator, as long as there has been no significant evidence of disease progression during the treatment interruption.\*

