**Table 7.2.4 Criteria for Disrupting Treatment, Dose Modification or Discontinuation**

Adverse Event	Agent most likely attributed to toxicity	Treatment modification
Immune Response to NSCs (i.e. development of a new neurologic deficit not attributed to the location of brain tumor, fever without localizing source of infection, new or progressive rash, cough etc.)		
Grade 2 allergic reaction to the NSCs.  NOTE: a decision to stop study treatment will be based on development of clinical signs/symptoms of an immune response rather than a particular level of anti-NSC T cells or antibodies.	NSCs	
Hold study treatment.
 
Initiate immunological testing: Take 3-5 ml of blood in red top tube, kept upright at room temperature until delivery to CICSL. Store at 4 C after sample clots if unable to deliver sample the same day. Take additional samples (at least one additional sample) every two days.
 
Initiate supportive care: Restart dexamethasone to a dose of 4 mg twice daily; if patient is already taking dexamethasone, then increase dexamethasone to at least 4 mg twice daily.
 
Hold study treatment until sign/symptoms <math>\leq</math> grade 1, and resume treatment at the same dose, while continuing dexamethasone at a dose determined by the discretion of the treating investigator in consultation with the PI.

Grade 3 or 4 allergic reaction to NSCs  NOTE: a decision to stop study treatment will be based on development of clinical signs/symptoms of an immune response rather than a particular level of anti-NSC T cells or antibodies.		Hold study treatment.  Initiate immunological testing: Take 3-5 ml of blood in red top tube, kept upright at room temperature until delivery to CICSL. Store at 4 C after sample clots if unable to deliver sample the same day. Take additional samples (at least one additional sample) every two days.  Initiate supportive care: Restart dexamethasone to a dose of 4 mg twice daily; if patient is already taking dexamethasone, then increase dexamethasone to at least 4 mg twice daily. Continue dexamethasone until event resolves to $\leq$ Grade 1, and thereafter at a dose determined by treating investigator as clinically indicated.  If an immune response to the NSCs is considered at least possible, discontinue study treatment
Hematological Toxicities		
Thrombocytopenia Grade 1 ( $75 \times 10^9/L < LLN$ )	Irinotecan	Maintain treatment

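### NSC allergic reactions are taken out of the DLT count and referred to the stopping rules, but no cohort-level count there triggers a review of the grade 3 or possibly related grade 4 reactions that end treatment

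*Combined protocol and SAP*

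**What the plan says.** Section numbers follow the table of contents and the protocol's own cross-references.

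- **Section 5.3.3 (Definition of DLT), closing note.** Allergic reactions to the NSCs are not DLTs, whatever their grade, because lowering the NSC dose would not be the right response. The note continues: "The possible occurrence of allergic reactions to the NSCs is addressed by the study stopping rules".
- **Section 5.6 (Study Stopping Rules).** Rule (ii), the only rule specific to allergy, stops the study after "two grade 4 allergic reactions that are probably or definitely related to NSCs". Rule (i) stops it when DLT-level toxicities with probable or definite attribution exceed 50% in more than 6 patients.
- **Table 7.2.4, grade 3 or 4 allergic reaction.** "If an immune response to the NSCs is considered at least possible, discontinue study treatment".
- **Section 5.3.4.** "The MTD/MFD will be based on the assessment of DLTs as defined in Section 5.3.3".
- **Section 5.4.** "If the DLT rate in the expansion cohort exceeds 34%, the toxicity data will be reviewed".
- **Section 5.3.3, criterion 1.** A patient has a DLT who "Receives less than 80% of study treatments due to a toxicity related to NSCs or irinotecan". The only exception listed there concerns CNS toxicities.
- **Section 5.3.2.** A patient counts for escalation after receiving at least 80% of each agent with 4 weeks of follow-up, or after a DLT. Otherwise "any study participant who is not evaluable for dose escalation will be replaced".

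**The concern.** The reason for the exclusion is sound: a smaller cell dose is not the remedy for an allergic reaction. The difficulty is that the section to which these reactions are referred takes up only a small part of them. A grade 3 reaction that ends treatment in cycle 1 would otherwise be a DLT under criterion 9, and DLT attribution normally starts at possible. Once excluded, the same event counts nowhere unless it is grade 4 and at least probable, or unless rule 5.6(i) is read by severity.

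This matters because immune response to these allogeneic, adenovirally transduced cells is a named risk (Section 7.1.2) and a secondary objective. The protocol states that the effect of repeat exposure is unknown, and repeat dosing begins at level 2. The counted rules, followed as written, could direct escalation or name an MFD after several patients at that level had treatment ended by such reactions.

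**Working it through.** **Nearest stated figures.** The plan attaches no figure to the allergy rule. Its detection figures for toxicity in general reproduce: 1 − 0.75^6 = 0.822 (stated about 82%) and 1 − 0.85^14 = 0.897 (stated about 90%).

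**Which rule counts which reaction**

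| Reaction ending treatment under Table 7.2.4 | 3+3, MTD/MFD, 34% review | 5.6(ii) | 5.6(i), read by severity |
|---|---|---|---|
| Grade 3, possible | no | no | no |
| Grade 3, probable/definite | no | no | yes |
| Grade 4, possible | no | no | no |
| Grade 4, probable/definite | no | yes | yes |

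**What happens to a cycle 1 reactor.** From level 2 the NSCs are given on Days 1 and 15 and irinotecan on Days 3 and 17. "Study agents are always held together, regardless of the attribution of the toxicity". A patient stopped before the second irinotecan dose has had 1/2 = 50% of it, below 80%. With the reaction excluded from the DLT definition, that patient is not evaluable and is replaced. A patient stopped after that dose and followed for 4 weeks counts as evaluable without a DLT. Either way the reaction adds nothing to the DLT count.

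**Illustration.** Assume 3 patients per level, no other DLTs, and grade 3 reactions starting after the Day 17 dose. Three of 3 reacting at level 2 reads as 0/3 DLTs and no events for 5.6(ii), so Section 5.3.2 directs escalation. On the severity reading with probable or definite attribution, 5.6(i) stands at 3/6 = 50% and does not fire. The next patient makes it 4/7 = 57% (fires) or 3/7 = 43% (does not).

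**Chance that 5.6(i) fires, severity reading.** Assume 3 reaction-free patients at level 1, then 3, 3 and 6 patients at levels 2 to 4 with a common reaction rate p, all probable or definite, and no other DLT-level toxicity. The count is updated patient by patient, and the rule fires when n > 6 and reactions/n > 0.5. For comparison, the chance of at least one cohort with 2 or more reactors is 1 − [1 − h(3)]² × [1 − h(6)], where h(n) = 1 − (1 − p)^n − n·p·(1 − p)^(n−1).

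| p | 5.6(i) fires (study stops) | 2 or more reactors in a cohort (review only) |
|---|---|---|
| 10% | 0.0002 | 0.16 |
| 20% | 0.004 | 0.47 |
| 30% | 0.03 | 0.74 |
| 50% | 0.27 | 0.97 |

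The columns describe different actions. The comparison shows how seldom the existing rule would act. It does not say that the study should stop more often. If all reactions are rated possible, the first column is 0 at every rate. If reactions occur only at level 4, 6 of 6 gives 6/15 = 40%: no stop, and the level is named MFD.

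**Chance that 5.6(ii) fires.** Let q be the rate of treatment-ending reactions and f the share that are grade 4 and probable or definite. The chance is h(29) with p = q·f. At q = 20% and n = 29 (about 5.8 patients taken off treatment) it is 0 for f = 0, 0.11 for f = 0.1, 0.43 for f = 0.25 and 0.80 for f = 0.5.

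**34% review.** Three reactors in 8 (37.5%), or 5 in 14 (35.7%), would pass 34%, but they add 0 to the DLT rate.

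**The case against.** The other side is substantial, and parts of it stand.

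*Different purposes.* Table 7.2.4 protects one patient and Section 5.6 ends the study. A lower threshold for the individual is normal. A reader might infer that the two rules contradict each other; they do not. The gap is that nothing lies between them.

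*No threshold at all.* A reader might infer this too, but it goes too far. Rule 5.6(i) speaks of DLT-level toxicities and sets its own attribution floor, so a severity reading is natural, and probable or definite reactions are then covered, though rarely decisively. If 14 patients are treated at level 4, it can fire even with reactions confined to that level, from 10/19 = 53%.

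*Events going unseen.* The documents do not support this. Table 11.4 sends serious grade 3 and 4 events to the DSMC within 5 or 10 days, including those rated possible. IND safety reports go to the FDA and the DSMC, and the analysis plan tabulates all toxicities by dose, severity and attribution. The first 3 patients at a level are staggered by 4 weeks, and the PMT decides on escalation. Patients with anti-HLA class I antibodies to the cells, or with prior NSC therapy, are excluded. Grade 2 reactions already require a hold and dexamethasone. These measures make events visible. None sets a cohort-level count that obliges a review.

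*Criterion 1.* A reader might infer a real conflict between the note and DLT criterion 1. On its plain wording the note covers the whole definition and prevails. Some doubt remains because criterion 1 has its own exception list, the note stands under the non-hematological heading, and Table 7.2.4 includes a new neurologic deficit among immune responses, which touches CNS criteria 5 to 7.

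*Low prior risk.* The first-in-human study of the parent line saw no grade 3 or 4 NSC toxicity, but after single doses.

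**Conclusion.** The gap is in the text and does not depend on any assumed rate: grade 3 reactions, and grade 4 reactions rated possible, can end treatment without counting in the 3+3, the MTD/MFD, rule 5.6(ii) or the 34% review. Rule 5.6(i) closes it only for probable or definite reactions, and then with chance 0.004 at a 20% rate and 0.27 at 50%. Those figures rest on the assumed cohort sizes, a common rate from level 2 and no other DLT-level toxicity. The documents give no reaction rate for this product.

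A reader might infer that an unsafe dose would become the RP2D. That does not follow, because the RP2D also rests on the full toxicity profile, including repeat dosing. What is missing is an obligation to pause and review. This is a cheap improvement to patient safety and worth making; confidence is medium.

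**What to change.** Keep the DLT exclusion and force no NSC de-escalation.

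1. **Sections 5.3.2 and 5.6.** If 2 patients in a 3- or 6-patient escalation cohort have, within the DLT window, an NSC allergic or immune reaction that ends treatment under Table 7.2.4, hold escalation and enrolment at that level until the PMT documents a review. Count reactors who have been replaced.
2. **Section 5.4.** Count such reactions together with DLTs toward the existing 34% review of the expansion cohort, with no separate 2-patient hold there. Two among up to 14 patients in any cycle would not be the 3+3 threshold, and at a 10% rate it would be reached with chance 0.42.
3. **Section 5.3.3.** Add one cross-reference confirming that the allergy note overrides criterion 1 but not CNS criteria 5 to 7.

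The cost is a few sentences and no new data. The downside is an occasional pause, which ends when the review is documented. From h(n) above, at an assumed 10% rate the chance is 0.03 per 3-patient cohort and 0.11 per 6-patient cohort; at 5% it is 0.01 and 0.03. With 3 patients at each of levels 1 to 3 and 6 at level 4, the chance of at least one hold at 10% is 1 − 0.972³ × 0.886 = 0.19.

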#### 5.1.4 Definition of Maximum Tolerated Dose and Maximum Feasible Dose

---

The MTD/MFD will be based on the assessment of DLTs as defined in Section 5.3.3. The MTD is the dose level at which 0/6 or 1/6 participants experience a DLT with the next higher dose having at least 2/3 or 2/6 participants encountering a DLT. If the MTD has not been reached with NSC dose level 4 and irinotecan schedule A, then that dose level will be termed the maximum feasible dose (MFD).

#### **Treatment Plan: Expansion Cohort**

---

After the MTD/MFD of the combination therapy is defined, an expansion cohort of 8 patients will be treated to gain more experience regarding the tolerability of study treatment at the MTD/MFD and to assess the biological activity of the hCE1m6-NSCs using intracerebral microdialysis. Since it is anticipated that the MTD/MFD will be 150 million NSCs (dose level 4), the 6 patients who will be treated on dose level 4 will undergo intracerebral microdialysis and be counted as part of the expansion cohort.

Four patients in the expansion cohort will undergo intracerebral microdialysis after receiving NSCs at the time of surgery followed 2 days later by IV irinotecan, but the other 4 patients in this cohort will not receive NSCs on the day of surgery. Instead they will be given IV irinotecan 2 days after surgery, and dialysate samples will be collected from them to determine how much SN-38 is present in the brain from treatment with IV irinotecan alone. These 4 patients will then receive their first dose of NSCs through the Rickham on day 15 of cycle 1 followed by irinotecan on day 17.

To determine who will receive their initial NSCs administration on the day of surgery, and who will receive their first NSC administration on Day 15 via the Rickham catheter, participants will be stratified according to surgery type (craniotomy or biopsy), and, as each group enrolls participants, it will alternate between enrolling the participant to the Day 1 NSC start date and the Day 15 NSC start date. For example, the first craniotomy participant will be assigned Day 1 NSC start date, the second craniotomy participant will be assigned Day 15 NSC start date, the third will be assigned Day 1 NSC start date, the fourth will be assigned Day 15 NSC start date, and so on as applicable. The same alternate enrollment scheme will apply to participants undergoing the biopsy procedure. The rationale for this plan is to ensure to the degree possible an even distribution of start dates for each surgery group which should increase the ability for direct comparison. There is no requirement for specific number of biopsy or craniotomy participants in the expansion cohort.

If the DLT rate in the expansion cohort exceeds 34%, the toxicity data will be reviewed.

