##### Nature of Illness and Treatment History

6. Histologically-confirmed diagnosis of a grade III or IV glioma (including glioblastoma, anaplastic astrocytoma, gliosarcoma, anaplastic oligodendrogloma, or anaplastic oligoastrocytoma), or has a prior, histologically-confirmed, diagnosis of a grade II glioma and now has radiographic findings consistent with a high-grade glioma (grade III or IV).
7. Imaging studies show evidence of recurrent tumor(s). If a patient is going to be enrolled to dose level two or higher, the patient must have a component of supratentorial disease (so as to enable placement of a Rickham reservoir/catheter) that is amenable to resection or biopsy.
8. High-grade glioma has recurred or progressed after prior treatment with brain radiation and temozolomide.
9. Participant must be in need of a craniotomy for tumor resection or a stereotactic brain biopsy for the purpose of diagnosis or differentiating between tumor progression versus treatment-induced effects following radiation therapy  $\pm$  chemotherapy.
10. Based on the neurosurgeon's judgment, there is no anticipated physical connection between the post-resection tumor cavity and the cerebral ventricles.
11. Neurosurgeon finds the prospective participant is able to undergo neurosurgery.
12. Any number of prior therapies is permitted. From the start of study treatment, the following time periods must have elapsed: 6 weeks from nitrosourea-containing chemotherapy, 4 weeks from non-nitrosourea-containing cytotoxic chemotherapy (except 23 days from last daily dose of temozolomide taken in a 5 of 28 day regimen), and 2 weeks from last dose of a targeted agent (except 4 weeks for bevacizumab). There is no time period requirement for prior radiation therapy.
13. Any clinically significant toxicity from prior therapy must have improved to grade 0 or grade 1.

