## 5 TREATMENT PLAN

This is an open-label Phase I study, with an expansion cohort once the MTD has been established. The schemas that follow provide an introduction of the treatment plan.

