## Assigning Treatment and Correlative Study Regimen

---

A participant's starting NSC dose level, irinotecan dose schedule, correlative study procedures, and NSC regimen will be assigned by the Principal Investigator based on the following criteria:

1. Except where planned in the expansion cohort, participants who do not receive Day 1 NSCs will be replaced.
2. During the 3+3 stage of the trial, any participants who are not evaluable for dose escalation will be replaced.
3. During the 3+3 stage of the trial, the NSC dose level (-1,1,2,3, or 4) and irinotecan dose schedule (A, B, or C) will be determined using criteria defined in Section 5.3.
4. The first six patients enrolled to the trial will have microdialysis catheters inserted and undergo microdialysis and accompanying blood plasma PK studies. If one or more of the six patients does not receive cycle 1 day 3 irinotecan, the patient(s) will be replaced with the next patient(s) enrolled.
5. During the expansion cohort, all eight participants will have microdialysis catheters inserted and undergo microdialysis and accompanying blood plasma PK studies. N.B., since it is anticipated that the MTD/MFD will be 150 million NSCs (dose level 4), the 6 patients who will be treated on dose level 4 will undergo intracerebral microdialysis and be counted as part of the expansion cohort.
6. During the expansion cohort, all 8 participants will follow the NSC dose level and irinotecan dose schedule per the MTD (or if the MTD is not reached, the MFD), however 4 participants will receive their initial NSC administration on the day of surgery (Day 1), and 4 participants will receive their first NSC administration on Day 15. Participants will be grouped according to surgery type (craniotomy or biopsy). As each group enrolls participants, it will alternate between enrolling the participant to the Day 1 NSC start date and the Day 15 NSC start date. (See Section 5.4 for further explanation).

Based on the above criteria, the Principal Investigator will communicate to the clinical research team and the neurosurgeon the assigned biopsy or craniotomy procedure A-K as detailed in table 8.2a and table 8.2b.

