- v. For immunological correlative studies: notify CICSL by e-mail to [[contact]](mailto:[contact]) at least 24 hours in advance of sampling. Collect six 6-ml lavender top (K-EDTA) tubes, keep on wet ice, and send to COH CICSL; collect approximately 10 ml of blood in red top tubes, keep upright at room temperature and process as per Section 8.6.1 before sending to the COH CICSL and Clinical Pathology. On days where study agent is administered, samples are always to be taken prior to agent administration.
- w. If participant is removed (or withdraws) from the trial prior to receiving study agent, the samples are to be discarded.
- x. Cycle 2 only.
- y. For RCR testing, collect two 6-ml lavender top (K-EDTA) tubes (or a volume of 10ml) maintained at room temperature with gentle agitation ~hourly and send to CICSL. On days where study agent is administered, samples are always to be taken prior to agent administration. Notify CICSL by e-mail to [[contact]](mailto:[contact]) in advance of sampling.
- z. RCR testing is required for all patients at 3 months\* and 6 months\* and annually\* thereafter post start of study treatment, whether patient is on treatment or in long term follow-up. For patients still on treatment, assuming there are no delays in treatment, this means RCR testing is to be performed at C4D1 and C7D1. Take RCR testing at most appropriate clinic visit for patients still on study treatment. For patients in long term follow-up, samples may be obtained via local physician and shipped to COH for testing. (\*+/-14 days)
- aa. CBC with ANC: hemoglobin, hematocrit, platelets, total WBC and neutrophils
- bb. Comprehensive metabolic panel: Sodium, potassium, chloride, carbon dioxide, creatinine, urea nitrogen, calcium, glucose, albumin, total bilirubin, alkaline phosphatase, total protein, ALG/SGPT and AST/SGOT.
- cc. Serum pregnancy test only for women of child bearing potential.
- dd. A contrast, non-contrast MRI is to be performed for screening within 28 days from registration. (Day 2 post-surgical MRI will serve as the baseline MRI).
- ee. A pre-surgical planning post-registration MRI **may** be performed if indicated by the neuro-surgeon.
- ff. A contrast, non-contrast MRI will be performed for all patients at least every two months.
- gg. A PET/CT scan will be performed within 7 days after surgery to serve as the baseline scan, and then a PET/CT scan will be performed whenever possible at the time follow up brain MRIs are done.

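### Day 1 or Day 15 NSC start is assigned by an open, printed alternation within surgery type, so the next arm can be known before a candidate is registered

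*Combined protocol and SAP*

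**What the plan says.** Section 5 describes the study in these terms: "This is an open-label Phase I study, with an expansion cohort once the MTD has been established". Under Section 5.2 the starting dose level, the correlative procedures and the NSC regimen "will be assigned by the Principal Investigator based on the following criteria". For the expansion cohort, item 6 of that section sets four Day 1 starters and four Day 15 starters and alternates between them within surgery type.

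Section 5.4 repeats the rule for each surgery group: "it will alternate between enrolling the participant to the Day 1 NSC start date and the Day 15 NSC start date". It then prints the order: "the first craniotomy participant will be assigned Day 1 NSC start date, the second craniotomy participant will be assigned Day 15 NSC start date", with the third and fourth following the same pattern. For the other group: "The same alternate enrollment scheme will apply to participants undergoing the biopsy procedure". The reason given is balance: "The rationale for this plan is to ensure to the degree possible an even distribution of start dates for each surgery group". The numbers of craniotomy and biopsy patients are left open.

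Inclusion criterion 9 reads "Participant must be in need of a craniotomy for tumor resection or a stereotactic brain biopsy". Note l to Table 10, on source documents for eligibility, includes the neurosurgeon's record that the patient needs a biopsy or craniotomy. Note dd adds: "A contrast, non-contrast MRI is to be performed for screening within 28 days from registration".

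The Sample Size section (15.1) powers the SN-38 comparison with a one-sided two-sample t test at 0.05, four per group, and calls the results exploratory. No section describes a random sequence, third-party assignment or concealment.

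**The concern.** Under strict alternation, anyone who knows a candidate's surgery type and how many patients that group already holds can name the next arm. The person who assigns the arm also leads the study, and the surgery need and a contrast MRI can be on file before registration. Foreknowledge could then affect who is approached, the order in which candidates are registered or, where there is a choice, which surgery is planned.

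At stake is the test of whether NSCs raise SN-38 in the brain. It is the plan's only concurrently controlled comparison with a stated power. The first six patients all receive NSCs, so they cannot act as controls. With four per arm, a chance or steered imbalance can hardly be adjusted for.

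The rule can also miss its own target. If each surgery group starts on Day 1, two odd-sized groups each supply one extra Day 1 patient.

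**Working it through.** **Inputs.** From the Sample Size section: log-scale difference 1.36, SD 0.66, four per group, one-sided 0.05, stated power 80%. From Sections 5.2 and 5.4: alternation within surgery type, target 4:4. The size of any steering effect is not in the documents and is assumed below.

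**1. The plan's own figure.** Noncentrality = 1.36 / (0.66 × √(1/4 + 1/4)) = 2.914, df = 6, critical t = 1.943. The noncentral t gives power 82.2%; three per group gives 66.7%. Four per group is thus the smallest size that reaches 80%, and the plan's number is reproduced. The log difference also checks: ln(7/1.8) = 1.358.

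**2. Predictability.** Given surgery type and the count in that group, the printed rule fixes 8 of 8 assignments. For biopsy this assumes the same starting arm as craniotomy, which the text suggests but does not state; once one biopsy patient is assigned, the rest follow.

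**3. Arm sizes.** With both groups starting on Day 1, Day 1 starters = ⌈c/2⌉ + ⌈b/2⌉ for c craniotomies and b biopsies.

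| Split (either way round) | Day 1 : Day 15 |
|---|---|
| 8+0, 6+2, 4+4 | 4 : 4 |
| 7+1, 5+3 | 5 : 3 |

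At 5:3, noncentrality = 1.36 / (0.66 × √(1/5 + 1/3)) = 2.822 and power is 80.0%.

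**4. Effect of steering on the test (illustration).** Suppose there is no true NSC effect but steering makes the arms differ by D standard deviations. The rejection probability is the noncentral t tail with noncentrality D × √2. The log shift is 0.66 × D and the fold shift is exp(0.66 × D).

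| Assumed D | Log shift | Fold | Error at SD 0.66 | Error, same fold, assumed SD 1.0 |
|---|---|---|---|---|
| 0.2 | 0.132 | 1.14 | 8.2% | 7.0% |
| 0.5 | 0.33 | 1.39 | 15.5% | 11.0% |
| 1 | 0.66 | 1.93 | 34.8% | 20.8% |

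The last column matters because the plan expects patients to vary more than the rats behind the 0.66. The D = 1 row is extreme: 0.66 / 1.36 is 49% of the planned effect, with all eight patients steered. If only half are steered at SD 0.66, the errors are 6.4%, 9.2% and 15.5%.

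**5. A concealed list in blocks of 2.** A guesser who knows the block size is right half the time on the first of each pair and always on the second, so expects 4 × 0.5 + 4 = 6 of 8, against 8 of 8 now and 4 by chance. Full steering effort then shifts the arms by (2 × 6 − 8)/8 = 0.5 of D, which gives the half-steered errors in step 4. An undisclosed block size makes guessing harder.

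**The case against.** The other side has a fair case. The comparison is secondary, four against four, declared exploratory and never called randomised. The method is disclosed and has a reason: NSC delivery differs between craniotomy and biopsy, so balance within surgery type matters. SN-38 is a laboratory measurement, which leaves little room for biased reading. The shifts in the illustration are assumed; with no steering the error stays at 5%. All of this stands and keeps the priority down. None of it supplies concealment, and balance by surgery type does not require a predictable sequence.

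It is also true that concealment up to registration closes only part of the gap. The surgeon is told the procedure letter before operating and then places one or two microdialysis catheters in residual tumor or peritumoral tissue. A list does not change that.

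A reader might go further and infer that the comparison is biased, or that the dose finding is compromised. The documents support neither: they show opportunity, not steering, and the DLT and MTD rules do not use this test. A reader might also infer a 6:2 comparison, since Sections 5.2 and 5.4 count the six dose level 4 patients in the cohort. That would need all six to have had Day 1 NSCs, and the same sections fix four and four. Who enters the allocation is unclear, but that is a separate matter of reconciliation.

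**Conclusion.** The point holds as a risk of selection bias from an unconcealed, predictable allocation, with low to moderate priority. Two things follow from the text: under the printed rule the next arm can be known before registration once surgery type is known, and nothing in the plan conceals it. The 5:3 result at odd splits rests on both surgery groups starting on Day 1 and costs little power (80.0% against 82.2%). The inflated error rates (8%, 16% and 35% at SD 0.66; 7%, 11% and 21% at SD 1.0) show how sensitive so small a test is to assumed shifts. They do not estimate what will happen. The plan's sample size figure itself is sound.

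**What to change.** In Sections 5.2 and 5.4, replace alternation with a random list stratified by surgery type in small blocks, held by someone outside the treating team. Keep the block sizes in a separate document, because the site reads the protocol. Release each assignment only after registration and surgery type are recorded. Cap assignments at four per arm. State whether a replacement takes the replaced patient's slot or the next unused entry; the first keeps the arm count simple but can be foreseen.

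This needs a short list and a few sentences, and no extra patients or procedures. Blocks of 2 keep surgery type evenly split between arms whenever both groups are even in size. At odd splits with a 4:4 cap, the arms differ by one craniotomy patient (25 percentage points, against 20 at 7+1 and 7 at 5+3 under alternation with its 5:3 arms). Small blocks also stay partly guessable, as step 5 shows.

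Because the surgeon will still know the arm, report catheter number, catheter site and surgery type by arm. If alternation is kept, state it as a limitation of the t test.

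Separately, reconcile Sections 5.2 and 5.4, which count the six dose level 4 patients in the cohort of eight, with the Sample Size section, which has eight additional patients and 14 in total, and say whether those six enter this allocation.
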